#### 11.1.2 Imputation Rules

Missing values will be treated as missing, except for the causality, intensity, seriousness and outcome of adverse events and for the definition of treatment emergent. For adverse events (AEs), a worst-case approach will be used: if causality is missing, the adverse event will be regarded as related to the IMP; if the intensity of an adverse event is missing, the adverse event will be regarded as severe; if seriousness is missing, the adverse event will be regarded as serious; if onset date is missing, it will be assumed to be at the date of Visit 2; if outcome is missing and no date of outcome is present, the outcome is regarded as 'ongoing' at the End-of-Trial Visit.

#### 11.1.3 Visit and Visit Windows

See Section 3.1.5 for visit windows.

## 11.2 Safety Endpoints of Special Interest

### 11.2.1 Hyponatraemia Episodes Based on Observed Serum Sodium Levels

#### 11.2.1.1 General Considerations

All tables and figures will be done for the overall trial population and by gender.

Observed serum sodium levels will both be summarized as a continuous variable and be used to define worst-case hyponatraemia episodes using the definitions specified in Table 7.

**Table 7 Definition of Hyponatraemia Episodes by Serum Sodium Range: Number of Consecutive Measurements of Serum Sodium below Upper Threshold Needed to Start Episode**

Degree	Serum Sodium Range (mmol/L)	Enrichment Period	Randomized-Treatment Period	
		Hyponatraemia Episode	Hyponatraemia Episode	'Confirmed' Hyponatraemia Episode
None	≥135	Not applicable (normal serum sodium level)		
Mild	≥130 to <135	1 st observation	1 st observation	3 rd consecutive observation
Moderate	>125 to <130	1 st observation	1 st observation	2 nd consecutive observation
Severe	≤125	1 st observation	1 st observation	1 st observation

### 11.2.1.2 Observed Serum Sodium Levels

Observed serum sodium levels and the change from baseline-ENR will be summarized by visit for the Safety-ENR analysis set. Observed serum sodium levels and the change from baseline-RT will be summarized by visit and treatment group for the Safety-RT analysis set.

All subjects in the Safety-ENR analysis set with a serum sodium value  $<130$  mmol/L at any time point will be listed by actual treatment group for the randomized period (non-randomized will be listed as a separate treatment group), including all serum sodium assessments by time point and including demographic data.

Graphs will present the serum sodium levels against analysis day (ADY) by treatment group and the subject profiles with a serum sodium level  $<135$  mmol/L at any time point during the trial will be highlighted. In addition, lowest observed serum sodium against age will be presented in two figures, one figure using plot symbols showing sex and one figure using plot symbols showing actual treatment group.

### 11.2.1.3 Hyponatraemia Episodes During the Randomized-Treatment Period based on Observed Serum Sodium Levels

When presenting occurrence (measured as number of subjects) by visit of worst-case hyponatraemia episodes as defined in [Table 7](#), all visits within the same visit window will be combined to define the worst-case hyponatraemia episode observed for the subject within the visit window. The occurrence of worst-case hyponatraemia episodes will be presented by treatment group and visit for the randomized-treatment period for the Safety-RT analysis set.

The number of the post-baseline-ENR ‘worst-case’ hyponatraemia episodes for each subject will be summarized overall and by visit as a categorical variable; here ‘worst-case’ for each episode is defined as the worst-case serum sodium level observed during the hyponatraemia episode.

In addition, the incidence of “Hyponatraemia Episode” ([Table 7](#)) per 1000 person-years at risk counting all events for a subject will be presented overall and by visit using the upper end of the visit window specified for Category I endpoints in [Table 4](#) as cut-points for the categorization of the at-risk time.

For each of the thresholds ( $<135$ ,  $<130$ , and  $\leq 125$  mmol/L), graphs presenting treatment-stratified Kaplan-Meier curves of time from randomization (Visit 4) to first serum sodium level below the threshold will be produced for the Safety-RT analysis set. The time to event is calculated as the date of the first serum sodium level below the threshold minus the date of randomization.

In addition, for the thresholds  $<135$  (mild to severe) and  $<130$  mmol/L (moderate to severe), treatment-stratified Kaplan-Meier plots corresponding to first ‘confirmed’ hyponatraemia episode will be produced. Here the date of confirmation is used as the date of the event. For mild to severe, the date of confirmation is the first of the dates of ‘3rd consecutive observation  $<135$  mmol/L’, ‘2nd consecutive observation  $<130$  mmol/L’, and ‘1st observation  $\leq 125$  mmol/L’. For moderate to

severe, the date of confirmation is the first of the dates of ‘2nd consecutive observation <130 mmol/L’ and ‘1st observation ≤125 mmol/L’.

In Kaplan-Meier plots, all subjects are censored at the earliest of End-of-Trial Visit and 85 days after randomization.

Since the event times are interval censored (the true time of crossing the threshold was after the time of the preceding serum sodium measurement and before or at the time of the current serum sodium measurement) and essentially grouped by the planned visits, the Kaplan-Meier plots are not quite appropriate. Therefore, event-free-time curves will also be produced based on life table methods using interval cut points derived as 1 + the largest observed event time within each of the visit windows specified for Category I endpoints in [Table 4](#).

Duration of the hyponatraemia episode will be derived as 1 + end date of episode – date of start of episode. For each threshold separately, the duration will be listed for serum sodium episodes defined as one or more observed serum sodium levels below the threshold. The listings will contain the duration, demographics, the day of stop of treatment relative to the start of the hyponatraemia episode, and the serum sodium values observed during the episode including the serum sodium value above 135 mmol/L defining the end of the hyponatraemia episode. For episodes starting before randomization, duration will be listed by sex for all subjects in the Safety-ENR analysis set. For episodes starting after randomization, duration will be listed by sex and treatment group for all subjects in the Safety-RT analysis set experiencing an episode of hyponatraemia based on observed serum sodium levels.

Nadir of observed serum sodium during hyponatraemia episodes will be illustrated by a graph including all hyponatraemia episodes and showing observed serum sodium levels against time since start of the hyponatraemia episode (time zero for an episode is defined as first time point with observed serum sodium below 135 mmol/L in the current episode).

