7.1.3.1 Serum Sodium

Serum sodium levels will be monitored throughout the trial as hyponatraemia is a potentially serious adverse drug reaction (ADR) associated with desmopressin treatment and may potentially be associated with FE 201836 treatment.

A central laboratory will be used. However, a local laboratory may be used in addition to the central laboratory if a quick turn-around time of the result is needed. In such case a sample must also be sent to the central laboratory. Evaluation of the laboratory-based eligibility criteria will be determined by the central laboratory results. All serum sodium values must be reviewed as soon as possible after the results are available. Any unexpected low serum sodium value must be re-tested. Any significant changes in serum sodium, judged by the investigator as clinically significant must be reported as adverse events, as described in Section 8.2.

Blood samples for analysis of serum sodium will be collected, preferably in the morning, at Visits 1, 3, 5, 6, 7 and 8, as presented in Table 6-1. The risk for subjects developing hyponatraemia during the trial period will be mitigated as follows (serum monitoring plan):

Screening (Visit 1)

All subjects must have normal serum sodium (≥ 135 mmol/L) at screening (Visit 1). If the serum sodium value is < 135 mmol/L (re-tested and confirmed, with results available within 7 days) the subject must be discontinued from the trial as a 'screening failure'.

Active Run-in Period

During the 1-week active run-in period, 4 days (± 1 day) after the planned start of IMP treatment, the subject will be telephoned to follow-up on safety.

Visit 3

At Visit 3 (after the active run-in), if the serum sodium value is < 130 mmol/L the investigator must immediately contact the subject and schedule visits for further evaluation. If the serum sodium value is < 130 mmol/L (re-tested and confirmed, with results available within 7 days) the subject will not be randomised to the trial and must be discontinued from the trial as a 'screening failure'. The subject will be followed (by the investigator) for safety until the serum sodium level is stable and not clinically significant, preferably until at least ≥ 135 mmol/L.

If the subject cannot attend Visit 3 as planned, arrangements must be made to test the serum sodium level at Day 6-8 from the IMP start date to ensure the serum sodium level is measured while the subject is taking IMP.

12-week Randomised Treatment Period

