For the screening period (the lifestyle-changes epoch, the active run-in epoch, and the washout epoch), the visit windows for all endpoints are linked to the start of the active run-in epoch (the baseline for the enrichment period), that is, the date of the scheduled Visit 2 (VISITNUM=2): All visits before the date of VISITNUM=2 are allocated to the Visit 1 window. All visits after the date of VISITNUM=2 and before the date of VISITNUM=4 are allocated to the Visit 3 window.

Prioritization between multiple visits with non-missing assessment of the endpoint within the same visit window for the screening period will be performed according the following rules, unless otherwise specified:

1. If the assessment is non-missing at the scheduled visit, the assessment at the scheduled visit is used.
2. If the assessment is missing at the scheduled visit, the non-missing assessment closest to the scheduled visit is used.
3. If the assessment is missing at the scheduled visit and the two closest, non-missing assessments from unscheduled visits in the same visit window have equal distances from the date of the scheduled visit, then the latest one will be selected (only relevant for Visit 3).

For the randomized, double-blind treatment epoch, different visit windows will be used for different endpoints. The endpoints fall mainly into two major categories according to when the endpoint is assessed.

Category I comprises efficacy and safety endpoints assessed at all visits during the randomized-treatment period. Efficacy endpoints are Number of Nocturnal Voids and Responder outcomes derived from number of nocturnal voids, NI Diary Total Score, NI Diary Overall Impact Score, PGI-I, PGI-S, Bother, FUSP, and Total Sleep. Safety endpoints are Hyponatremia Serum Sodium Level, Clinical Chemistry, Haematology, Urinalysis, Weight, and Vital Signs.

Category II comprises the efficacy endpoints assessed only at Visits 5 and 8: Nocturnal Diuresis Rate, NUV, and NPi; and the safety endpoint: Total Daily Urine Volume.

The remaining endpoints, the efficacy endpoints ISI and Copeptin and the safety endpoint Coagulation factors, are assessed at different visits. All visit windows for the randomized-treatment period are specified below ([Table 4](#)):

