**Table 4 Visit Windows Using Analysis Day Calculated as Site Visit Date – Date of Visit 4.**

Visit Number	Visit windows a			
	5	6	7	8
Visit Week	Week 1	Week 4	Week 8	Week 12
Planned Day According to Protocol	8	28	56	84
Target day b	7	28	56	84
Category I Endpoints	[1, 17]	[18, 42]	[43, 70]	[71, $\infty$ [
Category II Endpoints	[1, 45]	NA	NA	[46, $\infty$ [
ISI	NA	[1, 42]	[43, 70]	[71, $\infty$ [
Copeptin	NA	NA	NA	[1, $\infty$ [
Coagulation factors	NA	[1, 55]	NA	[56, $\infty$ [

a using analysis day derived from the corresponding site visit date

b to be used when prioritizing multiple assessments of an endpoint within the visit window

Prioritization between multiple visits with non-missing assessment of the endpoint within the same visit window will be performed according the following rules, unless otherwise specified:

1. If more than one non-missing assessment of an endpoint fall within the same visit window, the one closest to the target day will be used for that endpoint.
2. If two non-missing assessments in the same visit window have equal distances from the target day, the latest one will be used.

For the first safety interim analysis, the actual visit (VISITNUM) will be used. For the futility interim analyses, the site visit date and the visit windows specified in [Table 4](#) will be used.

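### The by-visit hyponatraemia rates use visit-window denominators that do not match the sodium sampling intervals, so the same risk reads about twice as high at Week 12 as at Week 8

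*SAP*

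**What the plan says.** SAP Section 11.2.1.3 adds to the by-visit counts an incidence of hyponatraemia episodes "per 1000 person-years at risk counting all events for a subject". This rate "will be presented overall and by visit using the upper end of the visit window specified for Category I endpoints" in Table 4 to divide the at-risk time.

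SAP Section 3.1.5 puts serum sodium in Category I: "Safety endpoints are Hyponatremia Serum Sodium Level, Clinical Chemistry, Haematology, Urinalysis, Weight, and Vital Signs". The Table 4 windows for that category are days 1 to 17, 18 to 42, 43 to 70, and 71 onwards with no upper limit. The target days are 7, 28, 56 and 84.

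Protocol Section 7.1.3.1 fixes the sampling: "Blood samples for analysis of serum sodium will be collected, preferably in the morning, at Visits 1, 3, 5, 6, 7 and 8". A footnote to SAP Table 3 adds a sodium value at Visit 4, which is analysis day 0. The scheduled samples from randomisation onwards therefore fall at about days 0, 7, 28, 56 and 84.

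Later in SAP Section 11.2.1.3 the event times are called interval censored, because "the true time of crossing the threshold was after the time of the preceding serum sodium measurement" and no later than the current one. For that reason the SAP supplements the Kaplan-Meier plots with life-table curves, whose cut-points lie one day after the last observed event in each window. This adjustment is made for the event-free-time curves only. The by-visit rates keep the window ends.

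**The concern.** The window ends are midpoints between adjacent target days. They suit the job of allocating a measurement to a visit. They do not suit a person-time denominator, because a sodium sample says nothing about the days after it and looks back only to the previous sample. Days 8 to 17 are charged to Week 1 although the scheduled Week 1 sample precedes them. Days 57 to 70 are charged to Week 8 although the Week 12 sample covers them.

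What is at stake is the time pattern. A by-visit rate adds to an overall rate only by showing when episodes occur, and hyponatraemia is the adverse event of special interest (Protocol Section 8.3). As specified, the table can show risk rising late in treatment when it is constant.

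**Working it through.** **Inputs.** Target days 7, 28, 56, 84 and window ends 17, 42, 70 (SAP Table 4). Day 0 sample at Visit 4 (SAP Table 3 footnote). The SAP does not say when at-risk time ends for this rate; day 84, the target day of the End-of-Trial Visit, is assumed.

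**Where the window ends come from.** (7+28)/2 = 17.5, (28+56)/2 = 42, (56+84)/2 = 70. These give the stated 17, 42 and 70.

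**Week 12 against Week 8, without a hazard model.** Both samples follow a 28-day gap. For k episodes found among N subjects at each visit, the displayed rates are k/(28N) and k/(14N), a ratio of 2.0. How long episodes last does not enter, because the gaps are equal. If the day-85 limit that the SAP sets for Kaplan-Meier plots were borrowed, the ratio would be 28/15 = 1.9.

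**Each visit against the true hazard, if every episode persists to the next sample.** Displayed/true = look-back days / denominator days.

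| Visit | Look-back | Denominator | Displayed/true |
|---|---|---|---|
| Week 1 | 7 | 17 | 0.41 (understated 17/7 = 2.4-fold) |
| Week 4 | 21 | 25 | 0.84 (understated 25/21 = 1.2-fold) |
| Week 8 | 28 | 28 | 1.00 |
| Week 12 | 28 | 14 | 2.00 |

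A constant hazard then shows as a rise of 2.00/0.41 = 4.9-fold.

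**Sensitivity to visit timing.** With Visit 5 between days 5 and 9, the Week 1 factor runs from 17/9 = 1.9 to 17/5 = 3.4. With Visit 8 between days 77 and 91 and Visit 7 between days 53 and 59, the Week 12 factor runs from (91−59)/(91−70) = 1.5 to (77−53)/(77−70) = 3.4.

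**Simulation.** 400,000 subjects, constant hazard (10% risk over 12 weeks, assumed), visit dates spread over the protocol windows, and 15% dropout with an early end-of-trial sample. Displayed/true was 0.43, 0.85, 1.01 and 1.99 by visit, and 0.99 overall.

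**If episodes can resolve between samples.** The documents give no episode duration. Assume exponential durations with mean D days. The number of new episodes found after a gap L is then proportional to D(1−exp(−L/D)). For D = 7 this is 4.42, 6.65, 6.87 and 6.87 for gaps of 7, 21, 28 and 28 days. The table divides these by three sets of denominators. The life-table set assumes last events at days 9, 31 and 59, so cut-points at days 10, 32 and 60.

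| Denominators (days) | Displayed/true by visit, D = 7 | Highest/lowest, D = 7 | Highest/lowest, persistent |
|---|---|---|---|
| SAP: 17, 25, 28, 14 | 0.26, 0.27, 0.25, 0.49 | 2.0 | 2.00/0.41 = 4.9 |
| Sample to sample: 7, 21, 28, 28 | 0.63, 0.32, 0.25, 0.25 | 2.6 | 1.0 |
| Life-table: 10, 22, 28, 24 | 0.44, 0.30, 0.25, 0.29 | 1.8 | (28/24)/(7/10) = 1.7 |

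At D = 7 the SAP's Week 1 rate is in line with Weeks 4 and 8, and only Week 12 stands out.

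**The case against.** The strongest objection is that the 2.4-fold figure for Week 1 depends on persistence. The SAP counts every episode and gives each one an end date, so episodes can resolve. With a mean length of 7 days the Week 1 discrepancy relative to Weeks 4 and 8 is gone, and sample-to-sample denominators would create an early peak of their own (2.6-fold). At a mean of 3 days that remedy has a spread of 3.6 against 2.0 for the SAP's rule. This stands. A reader might infer that Week 1 is understated whatever happens; the documents do not support that, because they give no episode duration. It does not touch the Week 12 against Week 8 result, which rests on equal gaps.

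Second, the days after a scheduled sample are not blind. Protocol Section 7.1.3.1 calls for unscheduled tests after a low value, with symptoms, after weight gain above 2 kg, or when certain medication is started or increased. This also stands: such tests would dilute the factors to an extent that cannot be computed from the documents.

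Third, the time course is shown elsewhere: subject counts by visit, sodium levels by visit and over time, listings of subjects below 130 mmol/L, and the life-table curves. The SAP's risk-benefit assessment (Section 13) rests on the therapeutic-window plots, which use incidence up to 12 weeks. A reader might infer that safety conclusions or the overall rate are compromised. They are not, and since all arms share the cut-points, comparisons between arms within a visit are largely preserved. The SAP also expects 20 subjects or fewer in several dose groups (Section 14), so by-visit rates within such arms will be noisy anyway. These points limit the importance; they do not make the denominators right.

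**Conclusion.** The concern holds, with a narrow scope. The by-visit denominators do not match the intervals that the scheduled samples cover, and the SAP recognises the interval censoring but adjusts only the curves for it.

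- Week 12 is inflated about 2-fold relative to Week 8 whatever the episode length, given visits near their target days and at-risk time ending near day 84. Against the true hazard the factor is about 1.5 to 3.4 with visit timing, if episodes persist.
- If episodes persist until the next sample, Week 1 is also understated about 2.4-fold and Week 4 about 1.2-fold, and a constant hazard looks like a roughly 5-fold rise. With short-lived episodes the Week 1 part shrinks or vanishes.
- All of this assumes that most new episodes are found at scheduled samples.

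Severity is minor: one supplementary descriptive safety table is affected, and no decision rule in the plan uses it.

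**What to change.** In SAP Section 11.2.1.3, for the by-visit rates only:

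- Replace the Table 4 window ends by the cut-points already derived for the life-table curves (just after the last observed event in each window), or by time from the previous scheduled sample to the current one. Sample-to-sample time is exact if episodes persist. The life-table cut-points are a compromise in the two cases tabulated above. Because they follow the observed events, one event found late in a window by an unscheduled test would move them back towards the window end, so they are better based on scheduled samples.
- Assign unscheduled samples to the interval in which they fall.
- State that at-risk time ends at the End-of-Trial Visit, and whether days inside an ongoing episode count as at risk.
- Add a footnote that the by-visit rates assume an episode lasts until the next sample.

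Keep the overall rate as planned. The cost is a few lines of SAP text and a small programming change, with no new data.

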4.4 Withdrawal Criteria

A subject must be withdrawn from the trial in case of:

- Serum sodium level is ≤ 125 mmol/L at any time point during the trial
- Significant non-compliance with the trial protocol, as judged by the investigator and/or the sponsor
- Other medical or safety reasons, as judged by the investigator and/or the sponsor
- The subject wishes to discontinue for any reason

A subject has the right to withdraw from the trial at any time for any reason, without the need to justify his/her decision. However, the investigator should record the reason for the subject's withdrawal, if possible. The investigator also has the right to withdraw a subject. Since an excessive rate of withdrawals can render the trial devoid of meaning, unnecessary withdrawal of subjects should be avoided.

Every effort should be made to invite subjects withdrawn/discontinued from the trial to an end-of-trial visit (Visit 8) as soon as possible after a decision of withdrawal/discontinuation has been taken. For any discontinuation, the investigator should obtain the required information and document the date and reason for the premature discontinuation in the eCRF.

In case the subject has withdrawn consent, no new data can be recorded in the eCRF. Correction of previous data and/or recording data related to visits/procedures done prior to but made available after withdrawal of consent (e.g., laboratory results) will be allowed unless the subject disapproves it.

If the reason for withdrawal is an adverse event, the specific event or the main laboratory abnormality must be recorded in the eCRF. The investigator should make thorough efforts to document the outcome.

Subjects discontinued from the trial will not be replaced, except for subjects randomised to treatment with 500 µg FE 201836 in case a decision is taken to decrease the maximum dose of FE 201836 from 500 µg to 350 µg (Section 4.2.2.1).

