During the 12 weeks randomised treatment period, any unexpected low serum sodium value (< 135 mmol/L or a drop in serum sodium level > 10 mmol/L) must be re-tested with at least 2 additional consecutive tests to identify the nadir and duration of the hyponatraemic episode. The serum sodium level should be re-tested within 5 (± 2 days) since the previous test. The subject will be followed (by the investigator) for safety until the serum sodium level is stable and not clinically significant, preferably until at least ≥ 135 mmol/L.

Any Time Point during the Trial

If the serum sodium value is ≤ 125 mmol/L at any time point during the trial, the treatment with the IMP must be stopped immediately and the subject must be withdrawn from the trial. All cases of serum sodium values ≤ 125 mmol/L will be reported as Serious Adverse Event (SAEs) (Section 8.5). The subject will be followed (by the investigator) for safety until the serum sodium level is stable and not clinically significant, preferably until at least ≥ 135 mmol/L.

Acute Intercurrent Illness

In case of acute intercurrent illnesses characterised by fluid and/or electrolyte imbalance (such as systemic infections, fever, gastroenteritis), the treatment with IMP should be interrupted until the subject has fully recovered. The treatment can be re-started at the discretion of the investigator once the condition of the subject is stabilised.

In addition, subjects may be called in for additional unscheduled visits due to safety reason, as described in Section 6.8.

Additional Serum Sodium Testing

Events that will trigger additional serum sodium testing include, but are not limited to, the following:

- If more than 21 days elapse from the serum sodium measurement at Visit 1 and the visit date of Visit 2, the serum sodium measurement must be re-tested, with results available prior to Visit 2.
- A subject is presenting with signs or symptoms of hyponatraemia (e.g., headache, dizziness)
- A subject has gained more than 2 kilograms in body weight between visits (Section 7.2.4)
- If concomitant treatment with therapy that may induce hyponatraemia (Section 4.3.1) is initiated or dosing of an existing therapy is increased during the trial, additional serum sodium monitoring should be performed in the first week (4-8 days) after initiation and again with follow-up as judged by the investigator, at least at 4 weeks.

7.1.3.2 von Willebrand Factor and Factor VIII

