9.10.3.1 Hyponatraemia during the Randomised Treatment Period

These analyses are restricted to the Safety Analysis Set only.

The incidence of the post-baseline worst-case hyponataemia episode for each subject will be summarised as described in [Table 9-6](#).

Graphs will plot the serum sodium levels by treatment group and the profiles of the subjects who at any time (Visit 1 and onwards) have a serum sodium level <135 mmol/L will be highlighted.

Kaplan-Meier plots of time from randomisation (Visit 4) to hyponatraemic serum sodium levels (<135, <130 and ≤125 mmol/L) per treatment group will be produced. For the thresholds <135 and <130 mmol/L at least 3 and 2 consecutive observations, respectively, have to be below the threshold to yield a hyponatraemic event ([Table 9-6](#)). For both cases the time is from randomisation until first observation below the respective limit that counts.

The associated relative hazards of treatment and gender will be analysed using Cox proportional hazards model adjusting for baseline serum sodium and age (<65, ≥65 years). Possible heterogeneity between the genders in the relative treatment hazards will be explored by the inclusion of a treatment-by-gender interaction term.

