In addition to the illustrations of the therapeutic window specified in the protocol, illustrations of the therapeutic window will be produced using the estimated treatment contrast compared to placebo for the change from baseline-RT to lowest post-baseline measurement of serum sodium as the safety indicator. The inclusion of desmopressin in the plots illustrating the therapeutic window (“Corresponding efficacy and safety of desmopressin will be illustrated in a side panel for comparison.”) has been deleted to comply with “None of the primary, secondary or explorative analyses will include desmopressin.” (Section 10.1).

In the analyses of time to ‘confirmed’ hyponatraemia episodes, the time to event is defined as the time of confirmation in stead of the time to first measurement below the threshold to avoid conditioning on the future. The protocol states “The associated relative hazards of treatment and gender will be analysed using Cox proportional hazards model adjusting for baseline serum sodium and age (<65,  $\geq$ 65 years). Possible heterogeneity between the genders in the relative treatment hazards will be explored by the inclusion of a treatment-by-gender interaction term”. These analyses will not be performed since the trial is too small to perform Cox regression analyses of the occurrence of hyponatraemia events with 9 treatment groups and 2 covariates.

The adverse events tables presenting incidences of least 5% have been changed to presenting at incidences of at least 10% because it is expected that for several of the FE 201836 treatment groups, 20 subjects or less are allocated to the group.

According to [REDACTED], the interim analyses will deviate from the Appendix 2 in the protocol regarding the derivation of the allocation probabilities by the factor  $1/(n_d + 1)$  before the normalization to sum to 1.

Remaining changes are all considered clarifications of presentations specified in the protocol.

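### In the two 'confirmed' hyponatraemia Kaplan-Meier plots, an episode above 125 mmol/L first seen at the End-of-Trial Visit can never count, so the plots understate confirmed risk

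*SAP*

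**What the plan says.** SAP 11.2.1.3 adds two treatment-stratified Kaplan-Meier plots of the first confirmed episode, one for <135 mmol/L and one for <130 mmol/L. SAP Table 7 sets the number of values needed: three in a row below 135, two in a row below 130, or a single value at or below 125. For timing, "Here the date of confirmation is used as the date of the event". The censoring rule follows: "In Kaplan-Meier plots, all subjects are censored at the earliest of End-of-Trial Visit and 85 days after randomization".

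The dating rule is a declared change. Protocol 9.10.3.1 had said: "For both cases the time is from randomisation until first observation below the respective limit that counts". It gave no censoring rule for these plots. SAP section 14 explains that the event time "is defined as the time of confirmation in stead of the time to first measurement below the threshold to avoid conditioning on the future". Neither SAP section says what the change does to episodes that begin at the end of follow-up.

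Protocol 7.1.3.1 schedules post-randomisation sodium at Visits 5, 6, 7 and 8. A value below 135, or a fall of more than 10 mmol/L, "must be re-tested with at least 2 additional consecutive tests to identify the nadir and duration of the hyponatraemic episode", with each re-test 5 ± 2 days after the one before. Under Protocol 4.4, subjects who leave early are invited "to an end-of-trial visit (Visit 8) as soon as possible after a decision of withdrawal/discontinuation has been taken", so their withdrawal visit is their End-of-Trial Visit.

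**The concern.** Dating the event at confirmation is reasonable in itself. The difficulty is that the censoring date was not adjusted to match. Confirmation of a non-severe episode needs one or two further samples taken days later. If the first low value is the End-of-Trial sample, those samples fall after the subject has been censored, even when every required re-test is done and every one is low.

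The loss always runs in one direction: it lowers the curve. Requiring consecutive values is also the protocol's own definition of a hyponatraemic episode in the randomised period (Protocol Table 9-6), and hyponatraemia is the adverse event of special interest. A reader who takes the right-hand end of these curves as the 12-week risk of a confirmed episode would read it too low. Nothing in the SAP warns of this.

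**Working it through.** The documents give no rate or sample size for these plots, so there is no figure to reproduce. The check is one of dates, followed by an illustration of size.

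**Inputs**
- Re-test gap: 5 ± 2 days, i.e. 3 to 7 days (Protocol 7.1.3.1).
- Values needed: second <130, third <135, first ≤125 (SAP Table 7 and 11.2.1.3).
- Censoring day: C = min(End-of-Trial Visit, day 85) (SAP 11.2.1.3).
- Visit days: 8 ± 2, 28 ± 3, 56 ± 3, 84 ± 7 (SAP Table 3).

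**1. Delay to confirmation.** Below 130: one gap, 3 to 7 days. Below 135: two gaps, 6 to 14 days.

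**2. First low value at the End-of-Trial Visit.** Let that visit be on day E, so C ≤ E. The earliest confirmation is E + 3 or E + 6, always later than C. Enumerating every in-window visit day and every allowed gap:

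| First low value at | <130 confirmed by C | <135 confirmed by C |
|---|---|---|
| Visit 5 (completer) | 375 of 375 | 1,875 of 1,875 |
| Visit 6 (completer) | 525 of 525 | 2,625 of 2,625 |
| Visit 7 (completer) | 525 of 525 | 2,625 of 2,625 |
| Visit 8 | 0 of 75 | 0 of 375 |

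The Visit 8 totals are 15 days × 5 gaps and 15 × 5 × 5. For an End-of-Trial Visit on any day from 1 to 91, which covers early withdrawal, the count is again 0. The counts do not change if analysis days run one behind protocol days.

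**3. The day-85 cap.** The Visit 8 window is days 77 to 91. Days 86 to 91 are 6 of its 15 days (5 of 15 if analysis days run one behind). A first low value taken then falls after C whatever its level. Values ≤125 are therefore lost too, and from the first-observation curves as well as the confirmed ones.

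**4. Size (assumptions, not document figures).**
- Equal new-onset chance p at each of four samples, all subjects complete, all re-tests done and confirming. Full risk is 1 − (1 − p)⁴; the curve shows 1 − (1 − p)³. For p = 1%, 3%, 5% and 10%, the curve shows 3.0%, 8.7%, 14.3% and 27.1% instead of 3.9%, 11.5%, 18.5% and 34.4%. The share lost is 25%, 24%, 23% and 21%.
- Constant onset hazard over 84 days: onsets on days 57 to 84 are found at Visit 8, so the share lost is 28/84 = 33%.
- Re-tests after Visit 8 are off drug. Let r be the chance that they confirm, relative to on-drug re-tests. For small p and equal detection, the share lost is r/(3 + r): 1/4 = 25% at r = 1, 0.5/3.5 = 14% at r = 0.5, 0.2/3.2 = 6% at r = 0.2.

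**The case against.** **Scope.** These are two supplementary, descriptive plots. The first-observation curves count Visit 8 lows up to day 85. The by-visit episode tables combine all samples in a window, and the Visit 8 window runs from day 71 with no upper limit (SAP Table 4), so later re-tests fall inside it. The person-time incidence uses first observations, and the listings and nadir graph cover all episodes. Risk-benefit (SAP 13) rests on the therapeutic-window figures, which use observed values <130 and ≤125 rather than confirmed episodes. The SAP itself calls its Kaplan-Meier plots imperfect because of interval censoring and adds life-table curves. It states no censoring rule for those, so whether they share the gap is unclear. All of this stands, and it sets the severity.

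**On-treatment reading.** The section concerns the randomised-treatment period, so stopping at its last visit is defensible. No drug is dispensed at Visit 8, and Protocol 1.3 gives FE 201836 a half-life of about 2 hours. Off-drug re-tests may well confirm less often. A reader might take 25% or 33% as the expected loss; the documents do not support that. These are the values at r = 1, and the documents give no r.

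**Withdrawals.** A reader might infer that subjects withdrawn for low sodium are censored because of the event, most of all in arms with more such withdrawals. The documents do not bear this out. Only ≤125 is a listed sodium trigger for withdrawal, and it needs one value. The withdrawal visit follows the decision, so a low value first seen there cannot have prompted it. If an earlier value <130 did, a second such value at the End-of-Trial sample confirms on the censoring date and counts. What remains is narrow: for example, a mild episode (130-134) or a symptom-led withdrawal cut short by the End-of-Trial Visit.

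**Same-day samples.** A local and a central sample at one Visit 8 might be read as two consecutive values <130. The SAP does not say that they count, and they could not supply three values <135 on the stated schedule.

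**Conclusion.** The point holds as a minor defect. Under the stated re-test interval, the confirmed Kaplan-Meier plots cannot count any episode above 125 mmol/L first seen at the End-of-Trial Visit. One of the four scheduled post-randomisation samples is therefore unable to start a countable non-severe episode, and the curves are biased downward. This follows from the SAP and protocol rules alone, apart from the same-day-sample ambiguity.

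The size does rest on assumptions. With off-drug re-tests confirming as often as on-drug ones, the share lost is about 25% under equal detection or 33% under a constant hazard. Lower off-drug confirmation brings the equal-detection figure to 14% or 6% at the assumed values of r. Onset clustered early in treatment would also reduce it.

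Two limits on the reading matter. The gap is not confined to values above 125, because the day-85 cap drops any first low value at an in-window Visit 8 on days 86-91, from both sets of curves. Nor does it undermine the trial's hyponatraemia reporting as a whole: other outputs still show these episodes, and no decision rule depends on the plots.

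**What to change.** In SAP 11.2.1.3:

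- For the two confirmed curves, count an episode whose first low value is at or before the End-of-Trial Visit and which the protocol-required re-tests confirm. Date it at the earlier of confirmation and the End-of-Trial Visit. Censor all other subjects at the End-of-Trial Visit.
- In all these Kaplan-Meier plots, replace the day-85 cap with the End-of-Trial Visit, or with day 91 as the end of the Visit 8 window. State the censoring date for a withdrawn subject who attends no End-of-Trial Visit, for whom the present rule leaves only day 85.
- Footnote that re-tests after Visit 8 are off drug, and show the curves under the present SAP rule as a check.
- State which censoring rule the life-table curves use.

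The subject stays at risk until the End-of-Trial Visit and leaves the risk set then in either case. Earlier risk sets are therefore unchanged, and the SAP's worry about conditioning on the future is largely met. It is not met fully: whether that exit is an event or a censoring is decided by later data. A few events will also rest on off-drug re-tests. The cost is a few SAP sentences and minor programming. No new data are needed, since the protocol already requires the re-tests, and nothing changes in treatment or monitoring.
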